4.1 Eligibility Criteria

4.1.1 Inclusion Criteria

Individuals must meet all of the following inclusion criteria in order to be eligible to participate in the study:

- Be female.
- Be diagnosed with cervical, vaginal or vulvar cancer.
- Be at least 18 years of age.
- If of child-bearing potential, must have a negative pregnancy test
- Be able to comply with study procedures.
- Have read and signed the IRB-approved Informed Consent form for participating in the study.

4.1.2 Exclusion Criteria

An individual who meets any of the following criteria will be excluded from participation in this study:

- Females who are pregnant or nursing.
- Patients who have received an investigational drug in the 30 days before study drug administration, or will receive one within 72 hours afterwards.

- Patients who are medically unstable, patients who are seriously or terminally ill, and patients whose clinical course is unpredictable. For example:
 - Patients on life support or in a critical care unit.
 - Patients with clinically unstable cardiac arrhythmias, such as recurrent ventricular tachycardia.
 - Patients with recent cerebral hemorrhage.
 - Patients who have undergone surgery within 24 hours prior to the study sonographic examination.
- Patients with congenital heart defects.
- Patient with a known allergy to Sonazoid (including an anaphylactic allergy to eggs or egg products).

4.2 Strategies for Recruitment and Retention

Potential research subjects will be identified by a member of the patient's care treatment team, the investigator or a research team member. Investigators will then screen the patient's medical records to determine the subject eligibility for study participation and discuss the study with the patient and their potential for enrolling in the research study. Consenting patients will be screened based on the inclusion/exclusion criteria above.

An investigator or research coordinator will explain the study to the patient. The patient will be given time to consider the risks and benefits of the study and ask questions about participation. The consent form will be reviewed with the patient and then the patient will be given the form to review. If consent interview is conducted by a coordinator, a study investigator will then discuss the study with the subject and answer any additional questions. The patient, person conducting study interview (if applicable), and a study investigator will all sign the consent form. The patient will be given a copy of the signed consent form for her records.

Trial participants will have the presence of inclusion criteria and absence of exclusion criteria verified by providing a medical history. A full demographic profile, known drug allergies or intolerances, and a review of the subject's medical/surgical history will be recorded. If the subject is a woman of childbearing potential, she will have a urine pregnancy test (the results of which will be made available to the subject prior to study initiation).

4.3 Participant Withdrawal

4.3.1 Reasons for Withdrawal

Participants are free to withdraw from participation in the study at any time upon request.

An investigator may terminate a study participant's participation in the study if:

- Any clinical adverse event (AE), laboratory abnormality, or other medical condition or situation occurs such that continued participation in the study would not be in the best interest of the participant.
- The participant meets an exclusion criterion (either newly developed or not previously recognized) that precludes further study participation.

4.3.2 Handling of Participant Withdrawals and Participant Discontinuation of Study Intervention

Trial participation will be considered completed if the subject has met all of the following trial requirements:

- Has received one set of subdermal injections of Sonazoid
- Has undergone the complete ultrasound imaging study as described in this protocol

If a subject's participation in the trial is interrupted for any reason (e.g., because of an AE) and the subject has met the criteria described above for completing the trial, the subject's trial participation will be considered completed. If a subject's trial participation is interrupted for any reason by the subject's or investigator's choice and the subject has not met all of the criteria listed above, then the subject will be considered a discontinued subject.

4.4 Premature Termination or Suspension of Study

This study may be suspended or prematurely terminated if there is sufficient reasonable cause. Written notification, documenting the reason for study suspension or termination, will be provided by the suspending or terminating party to the IRB and the FDA. If the study is prematurely terminated or suspended, the principal investigator will promptly inform the IRB and will provide the reason(s) for the termination or suspension.

Circumstances that may warrant termination include, but are not limited to:

- Determination of unexpected, significant, or unacceptable risk to participants.
- Insufficient adherence to protocol requirements.
- Data that is not sufficiently complete and/or evaluable.
- Determination of futility.

5 Study Intervention

5.1 Study Product

The UCA Sonazoid consisting of gas-filled microbubbles will be used in this study. Our existing FDA Investigator IND (# 127,419) on subdermal injections of Sonazoid will be amended to include this project. This IND was originally set up for breast cancer and was subsequently amended to also include esophageal cancers. Studies will not commence until regulatory approval has been obtained from the FDA as well as the IRB committee for TJU. The clinical trial will also be registered with ClinicalTrials.gov.

5.2 Study Product Description

Sonazoid is a sterile non-pyrogenic suspension of microspheres of lipid stabilized perfluorobutane (PFB) for contrast-enhancement, with a median diameter between 2.4 and 3.5 μm and less than

0.1 % larger than 7 μm . Sonazoid is formulated as a powder for injection consisting of lyophilized sucrose entrapping hydrogenated egg phosphatidyl serine (HEPS) PFB microspheres under a PFB headspace. Each milliliter of Sonazoid contains roughly 1.2 billion microspheres.

5.2.1 Acquisition

Sonazoid will be provided by GE Healthcare (Oslo, Norway) free of charge (similar to our other protocols involving this UCA).

5.2.2 Formulation, Packaging, and Labeling

Sonazoid is supplied as a dry powder within 10 mL sealed vials. The headspace of the vials contains PFB. A single vial with 16 μL of Sonazoid microbubbles (2 mL) will be prepared for each subject by resuspending each vial in 2 mL of injection grade water supplied by GE. Each kit will be labeled with the study number as well as vial lot and batch numbers. All materials and supplies used for the subdermal injection procedure will be identical to those described in GE Healthcare's current Sonazoid IND.

Packages will contain the following medical grade, sterile and non-pyrogenic components:

[figure not shown]
- SonazoidTM Powder for Injection, 16 μL microbubbles per vial;
- Sterile water for reconstitution of SonazoidTM
- CODAN Chemospike (contains 0.20 μm air filter and 5 μm liquid filter)

5.2.3 Product Storage and Stability

Sonazoid will be stored in a secure cabinet, with only the study investigators and research personnel having access. The study researchers will be responsible for drug reconstitution and inventory control. New vials must be prepared for each subject's contrast administration and will be used immediately upon reconstitution. Sonazoid is stable for 4 hours after reconstitution. If the agent is suspended and not used within 4 hours it will be discarded.

5.3 Dosage, Preparation, and Administration

- Perforate the stopper of the Sonazoid vial with the provided CODAN Chemospike.
- Remove protective cap from the syringe port of the Chemospike.
- Using a 2-mL syringe, add 2 mL sterile water through the Chemospike.
- With the syringe remaining attached to the Chemospike, **immediately** shake the product for 1 minute to ensure a homogeneous product.
- Withdraw the product into the syringe and re-inject the product back into the vial again. This is to avoid dilution of the product due to the dead-space volume in the Chemospike.
- Remove the syringe from the syringe port and reattach the protective cap. The concentration of the reconstituted product is 8 μL microbubbles/mL.

Each subject will receive a 1 ml subdermal dose of Sonazoid divided into four individual aliquots at four locations (12, 3, 6, and 9 o'clock) around the primary tumor using 20-22 gauge cannula.

5.4 Dose Modifications and Dosing Delays

Not applicable for this study.

5.5 Study Product Accountability

A log of study drug will be kept by the research coordinator on this study. All vials released for studies will be recorded. Unused drug and empty vials will be properly disposed of after reconciling in the log of study drug.

5.6 Dietary Restrictions

No special dietary or "life-style" requirements are applicable.

5.7 Study Procedural Intervention(s) Description

Screening Assessments

Screening assessments will be performed within 4 weeks prior to the administration of Sonazoid. All subjects will receive a written consent form and a verbal explanation of the trial by the investigator and/or the research study coordinator and will be asked to sign the written informed consent. Participants will have the presence of inclusion criteria and absence of exclusion criteria (cf., sections 4.1.1 and 4.1.2) verified by providing a comprehensive medical history, which will include screening assessments for their cervical, vaginal or vulvar cancer diagnosis.

Medical History

A full demographic profile, known drug allergies or intolerances, and a review of the subject's medical/surgical history will be recorded. If the subject is of childbearing potential, she will have

a urine pregnancy test (the results of which will be made available to the subject prior to study initiation).

5.8 Administration of Procedural Intervention

Administration of Sonazoid will be performed under direct supervision of a medical doctor. Emergency services (e.g., a crash cart) will be available within the hospital in case of any acute adverse reactions. Additionally, resuscitation equipment will be in immediate proximity to the patient. Patients will be monitored for AEs post Sonazoid treatment for a minimum of one hour. Trained CPR personnel and resuscitation equipment will be in attendance during this monitoring period. A dose of one vial with 16 μ l of Sonazoid microbubbles (2 ml total after resuspension) will be prepared for each subject by resuspending each vial in 2 ml of injection grade water supplied by GE (as described in section 5.3). All materials and supplies used for the infusion procedure will be identical to those described in GE Healthcare's current Sonazoid IND. Each subject will receive 1 ml subdermal dose of Sonazoid divided into four individual aliquots of 0.25ml at four locations (12, 3, 6, and 9 o'clock) around the primary tumor using a 20-22 gauge cannula.

Ultrasound Imaging (lymphosonography)

The ultrasound examinations will be performed by a qualified sonographer or physician. Procedures and equipment for this trial will be used in accordance with typical clinical procedures. All trial procedures will be conducted in accordance with Good Clinical Practice. An Aplio i800 scanner with a curvilinear (8C1), a linear (18L5) and an endovaginal (11C3) probe CEUS will be used during the study. The patients will undergo an ultrasound examination to locate the tumor where a baseline grayscale and color Doppler ultrasound scan of the lesion will be obtained. Sonazoid will be administrated via subdermal injection in 4 aliquots at 12, 3, 6, and 9 o'clock positions around the primary tumor, with 0.25 ml for each aliquot adding to a total dose of 1.0 ml. Real time CEUS will then be performed to identify the number, location and course of the LCs drainage from the tumor to the SLNs. All LNs that demonstrate contrast-enhancement will be considered SLNs and their locations, depth beneath the skin surface and size (measured in three orthogonal dimensions) will be recorded and compared to the standard of care (i.e., to pathology or PET-CT). Digital clips of the ultrasound study will be acquired.

Contraindications

Sonazoid should not be administered to patients with known or suspected hypersensitivity to egg phosphatidyl serine. Patients with a history of anaphylactic allergy to eggs or egg products will be excluded from the study.

Safety Assessments

Emergency services (e.g., a crash cart) will be available within the hospital in case of any acute adverse reactions. Adverse events will be monitored during the entire procedure.

5.9 Administration of Procedural Intervention

Each subject will receive a 1 ml subdermal dose of Sonazoid divided into four individual aliquots at four locations (12, 3, 6, and 9 o'clock) around the primary tumor using 20-22 gauge cannula by the Ultrasound Research team (consisting of MDs (radiologists and gynecological oncologists),

sonographers, RNs, basic scientists and research coordinators). We anticipate each session will take approximately 45 min out of which around 25 min will be the actual scanning time.

5.10 Procedures for Training of Clinicians on Procedural Intervention

The personnel performing the lymphosonography procedures are all from the Ultrasound Research lab or Gynecological Oncology and have extensive experience with injections as well as CEUS and ultrasound imaging procedures. These individuals will all receive training by the PI in this specific protocol.

6 Study Schedule

6.1 Screening

Assess patient eligibility, complete appropriate screening procedures and evaluations prior to study entry.

- Obtain informed consent
- A qualitative urine pregnancy test, for female patients of childbearing potential.

6.2 On Study Period

The ultrasound examinations will be performed by a qualified sonographer or physician. Procedures and equipment for this trial will be used in accordance with typical clinical procedures. All trial procedures will be conducted in accordance with Good Clinical Practice. An Aplio i800 scanner with a curvilinear (8C1), a linear (18L5) and an endovaginal (11C3) probe CEUS will be used during the study. The patients will undergo an ultrasound examination to locate the tumor where a baseline grayscale and color Doppler ultrasound scan of the lesion will be obtained. Sonazoid will be administrated in 4 aliquots at 12, 3, 6, and 9 o'clock positions around the primary tumor, with 0.25 ml for each aliquot adding to a total dose of 1.0 ml. Real time CEUS will then be performed to identify the number, location and course of the LCs drainage from the tumor to the SLNs. All LNs that demonstrate contrast-enhancement will be considered SLNs and their locations, depth beneath the skin surface and size (measured in three orthogonal dimensions) will be recorded and compared to the standard of care (i.e., to pathology or PET-CT). Digital clips of the ultrasound study will be acquired.

6.3 End of Treatment Study Procedures

Trial participation will be considered completed if the subject has met all of the following trial requirements:

- Has received one set of subdermal injections of Sonazoid
- Has undergone the complete ultrasound imaging study as described in this protocol

6.4 Withdrawal Visit/Discontinuation of Therapy

If a subject's participation in the trial is interrupted for any reason (e.g., because of an AE) and the subject has met the criteria described above for completing the trial, the subject's trial

participation will be considered completed. If a subject's trial participation is interrupted for any reason by the subject's or investigator's choice and the subject has not met all of the criteria listed above, then the subject will be considered a discontinued subject.

7 Study Procedures and Evaluations

7.1 Study Procedures/Evaluations

As outlined in section 5.7:

- Medical history
- Lymphosonography

8 Evaluation of Safety

8.1 Specification of Safety Parameters

8.1.1 Unanticipated Problems

Unanticipated problems (UAPs) include, in general, any incident, experience, or outcome that meets the following criteria:

- unexpected in terms of nature, severity, or frequency given (a) the research procedures that are described in the protocol-related documents, such as the IRB-approved research protocol and informed consent document; and (b) the characteristics of the participant population being studied;

UAPs are considered to pose risk to participants or others when they suggest that the research places participants or others at a greater risk of harm (including physical, psychological, economic, or social harm) than was previously known or recognized.

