8.4.1 Reporting to IRB

8.4.1.1 *Unanticipated Problems*

All incidents or events that meet criteria for unanticipated problems (UAPs) as defined in Section 8.1.1 Unanticipated Problems require the creation and completion of an unanticipated problem report form (OHR-20).

UAPs that pose risk to participants or others, and that are not AEs, will be submitted to the IRB on an OHR-20 form via the eazUP system within 10 working days of the investigator becoming aware of the event.

UAPs that do not pose risk to participants or others will be submitted to the IRB at the next continuing review.

8.4.1.2 *Adverse Events*

Grade 1 AEs will be reported to the IRB at continuing review.

Grade 2 AEs will be reported to the IRB at the time of continuing review.

8.4.1.3 *Serious Adverse Events*

SAEs will be reported to the IRB on OHR-10 forms via the electronic reporting system (eSAEY) according to the required time frames described below.

Grade 3-4 AEs that are unexpected and deemed to be at least possibly related to the study will be reported to the IRB within 2 working days of knowledge of the event.

Grade 3-4 AEs that are deemed unrelated to the study will be reported to the IRB within 5 working days.

Grade 5 AEs will be reported to the IRB within one working day of knowledge of the event.

All SAEs will be submitted to the IRB at continuing review, including those that were reported previously.

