8.4.1 Reporting of Pregnancy

Pregnancy is an exclusion criteria.

Table 2: DSMC AE/SAE Reporting Requirements

	Grade 1	Grade 2		Grade 3				Grades 4 and 5
	Unexpected and Expected	Unexpected	Expected	Unexpected		Expected		Unexpected and Expected
				With Hospitalization	Without Hospitalization	With Hospitalization	Without Hospitalization	
Unrelated Unlikely	Reviewed at Quarterly DSMC Meeting and IRB Annual Review	Reviewed at Quarterly DSMC Meeting and IRB Annual Review	Reviewed at Quarterly DSMC Meeting and IRB Annual Review	5 Working Days	Reviewed at Quarterly DSMC Meeting and IRB Annual Review	5 Working Days	Reviewed at Quarterly DSMC Meeting and IRB Annual Review	Phase I - 48 Hours (Death: 24 Hours)
Possible Probably Definite	Reviewed at Quarterly DSMC Meeting and IRB Annual Review	Reviewed at Quarterly DSMC Meeting and IRB Annual Review	Reviewed at Quarterly DSMC Meeting and IRB Annual Review	48 Hours (Death: 24 Hours)	Phase I - 48 Hours	48 Hours (Death: 24 Hours)	Reviewed at Quarterly DSMC Meeting and IRB Annual Review	Phase I and Phase II - 48 Hours (Death: 24 Hours)

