15.5 Protocol Deviations

A protocol deviation is any noncompliance with the protocol, International Conference on Harmonization (ICH), Good Clinical Practice (GCP) and protocol-specific guidelines. The deviation (any activity conducted outside the parameters established by the protocol) may be either on the part of the participant, the investigator, or the study site staff and may or may not pose a risk to participants or others or may affect the integrity of the data obtained from the study.

The risk posed by the deviation, to the study or the study participant gives rise to an Unanticipated problem (UAP). It is crucial to document the deviation/unanticipated problem in the protocol deviation log (Appendix D) and submitted to the IRB as per the sites regulations. As a result of deviations, corrective actions are to be developed and implemented promptly.

UAPs and protocol deviations that pose risk to participants or others, and that are not AEs, or that affect study integrity will be submitted to the IRB via the <ezUP system> within 5 working days of the investigator becoming aware of the event.

UAPs and protocol deviations that do not pose risk to participants or others and do or do not affect study integrity must be entered in the deviation log (Appendix D) and submitted to the IRB at the next continuing review.

GE Healthcare will be informed of all AEs within 48 hours. In addition all unexpected SAEs are reported to the TJU IRB, the SKCC DSMB and to the FDA.

Relationship to Sonazoid Administration

The relationship or association of the AE to the Sonazoid administration will be characterized as "unlikely," "possible," or "probable." A relationship assessment will be performed by the investigator to determine if an AE is attributable to Sonazoid and will be recorded on a data form. The investigator will refer to the Sonazoid investigator brochure for assistance in determining AE relationship.

An "unlikely" relationship indicates that there is little or no chance that Sonazoid caused the reported AE; other conditions, including concurrent illnesses, progression or expression of the disease state, or a reaction to a concurrent medication, appear to explain the reported AE.

A "possible" relationship indicates that the association of the AE with Sonazoid is unknown. However, the AE is not reasonably attributed to any other condition.

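### A non-serious grade 1-2 adverse event that signals new risk has no timed report to the IRB, because the unanticipated-problem deadlines exclude all adverse events

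*Combined protocol and SAP*

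**What the plan says.** All references are to the combined protocol and SAP.

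- **Definition (8.1.1).** A UAP is any incident, experience or outcome that is "unexpected in terms of nature, severity, or frequency given" the described procedures and the population studied. AEs are not carved out. UAPs are held to pose risk "when they suggest that the research places participants or others at a greater risk of harm" than was previously known.
- **Timed rule (8.4.1.1).** An OHR-20 form must be completed for every UAP. The deadline is narrower: "UAPs that pose risk to participants or others, and that are not AEs, will be submitted to the IRB on an OHR-20 form", and this must happen "within 10 working days of the investigator becoming aware of the event". UAPs that pose no risk wait for the next continuing review.
- **Second timed rule (15.5).** The same exclusion of AEs appears, with a limit of 5 working days. A separate branch covers events that affect study integrity.
- **AE rule (8.4.1.2).** Grade 1 AEs go to continuing review. For grade 2, "Grade 2 AEs will be reported to the IRB at the time of continuing review". Neither sentence makes an exception for unexpected or related events.
- **Table 2.** For grade 1 events, and for unexpected grade 2 events, rated possible, probable or definite, the entry is "Reviewed at Quarterly DSMC Meeting and IRB Annual Review".
- **Other recipients.** Section 8.4.2 sends all AEs to the DSMC. Section 15.5 adds: "GE Healthcare will be informed of all AEs within 48 hours".

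**The concern.** The greater-risk test in 8.1.1 exists to separate problems the IRB should hear about soon from those that can wait. For a non-serious grade 1-2 AE the test changes nothing: once the event is an AE it leaves the timed UAP route, and the AE route sorts by grade alone. An AE judged to show a new risk is then reported to the IRB no sooner than a UAP judged to show none.

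The stake is that the IRB approves the consent form (14.2). The subdermal safety evidence the protocol describes is a study of 12 healthy volunteers injected in the breast (1.1 and 8.1.2, Table 1). This trial injects around cervical, vaginal or vulvar tumours, a different site and population. If an unexpected low-grade reaction appears there, further women may consent and be dosed before the IRB has seen it.

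**Working it through.** The plan gives no figure to reproduce on this point. The check follows one case, a non-serious grade 1 or 2 AE that is unexpected, at least possibly related and meets the 8.1.1 greater-risk test, through each reporting rule.

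| Rule | Applies to this case? | Time to the IRB |
|---|---|---|
| 8.1.1 definition | Yes; 8.3.2 defines an unexpected AE by the same three attributes, and 8.4 refers to AEs reportable under 8.1.1 | None stated |
| 8.4.1.1, OHR-20 form | Yes, for every UAP | None stated when the UAP is an AE |
| 8.4.1.1, risk-posing UAP | No, because it is an AE | (10 working days) |
| 15.5, risk-posing UAP | No, unless it is held to affect study integrity, which is not a safety test | (5 working days) |
| 8.4, SAE rule | No, because it is non-serious | (24 hours) |
| 8.4.1.3, unexpected related grade 3-4 | No, because of its grade | (2 working days) |
| 8.4.1.2, grade 1-2 AE | Yes | Continuing review |
| Table 2 | Yes | Annual review |

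Only the last two rows give an IRB time for this case. Appendix A (Investigator Obligations, item A) lets the IRB set the review interval, with at least one review a year, so 12 months is the ceiling.

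**Women dosed before the IRB is told**

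Inputs: 40 women and 24 months of recruitment (4 and 11.2). Assumptions: even accrual, one dosing session per woman close to enrolment, and events equally likely at any time between reviews.

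- Accrual rate: 40 / 24 = 1.67 women per month.
- Annual IRB review, longest wait: 1.67 × 12 = 20 women.
- Annual IRB review, average wait of half the interval: 1.67 × 6 = 10 women.
- A six-month IRB interval, shown only for range: 10 at most and 5 on average.
- UAP timeline, taking 24 months as 104 weeks: 40 / 104 = 0.38 women per week. Five working days (one week) gives 0.38 and ten working days (two weeks) gives 0.77, so fewer than one on average even if the whole limit is used.
- DSMC, for comparison: 1.67 × 3 = 5 women per quarter at most, about 2.5 on average.

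**The case against.** The strongest reply is that this is deliberate tiering. Section 8.1.1 is a definition and promises no timeline. Both timed rules hand AEs to the AE rules, where timing follows grade, and by the CTCAE text in 8.3 a grade 1 event needs no intervention and a grade 2 event only minimal, local or noninvasive intervention. Periodic IRB review with quarterly DSMC review is a coherent choice for ordinary events of that kind. That stands for most grade 1-2 AEs. It does not meet the case of one already judged to suggest a greater risk than was known, since there the plan's own test has been met and has no effect on IRB timing.

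Other routes exist, but none gives the IRB a deadline for these events:

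- The OHR-20 form is required, without a submission time.
- Section 8.5 lists AEs of a kind not previously known as grounds to discontinue the trial, with no grade threshold. It is discretionary, and the IRB notice in 4.4 follows only an actual suspension or termination.
- An important medical event may be judged an SAE (8.1.3) and then go to the IRB within 24 hours. This narrows the class to events judged non-serious; it does not empty it.
- The DSMP and the site regulations that the protocol refers to may say more. They are not available here. The protocol's explicit table entries are what staff will follow.

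Two stronger readings are tempting. A reader might infer from 8.4.2 that the DSMC sees these events only if the PI, who is also the sponsor, chooses. The documents do not support that: the section sends all AEs to the DSMC, and the PI's opinion governs only additional unanticipated problems. A reader might also infer that an unexpected low-grade local reaction is the likeliest new signal. No passage gives such a likelihood, and redness, pain, bruising, burning, numbness and tingling are already listed. New nature, severity or frequency is possible, and the point needs no more than that.

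**Conclusion.** The point holds for non-serious grade 1-2 AEs that are unexpected, at least possibly related and meet the 8.1.1 greater-risk test. For them the plan states a rule, not merely an omission, and that rule defers IRB notice to continuing review. Serious events are not affected, and unexpected, related grade 3-5 AEs have their own shorter IRB limits. The DSMC and the manufacturer are informed, so the gap is IRB notice alone.

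The size is up to about 20 women, half the trial, and about 10 on average under annual review, against fewer than one on average under either UAP limit. A reader might take 20 as the expected number. It is the maximum: it needs the event to fall just after a review and the interval to be a full year. The figures rest on even accrual and would be smaller if the IRB sets a shorter interval.

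This should be corrected. It does not bear on the sample size or the efficacy analysis.

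**What to change.** 1. In 8.4.1.1 and 15.5, state that an AE of any grade that is unexpected, at least possibly related and meets the 8.1.1 greater-risk test is submitted to the IRB on the UAP timeline, and that this does not lengthen any shorter limit already set for grade 3-5 AEs or SAEs. Simply striking the exclusion of AEs would be worse, because it would set a 5- or 10-working-day limit beside those shorter ones without saying which governs.
2. Cross-reference this in 8.4.1.2 and in a footnote to the grade 1 and grade 2 cells of Table 2.
3. Reconcile the limits in 8.4.1.1 (10 working days) and 15.5 (5 working days), so that there is one UAP timeline to refer to.

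The cost is wording in three sections and one table footnote. The downside is a few extra OHR-20 submissions in a 40-patient study. Ordinary grade 1-2 AEs stay on their present schedule.
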